7.3 Software Version

All analyses will be conducted using SAS version 9.4. Other statistical packages that can be used are SPSS version 19.0 or higher.

8. STATISTICAL CONSIDERATIONS

8.1 Statistical Bias Reduction

Methods for handling bias will be discussed in the appropriate section for endpoints relating to missing values.

8.2 Statistical Tests and Confidence Intervals

Unless otherwise specified in the description of the analyses, a two-sided 95% confidence interval will be considered as a default ($\alpha = 5\%$). P-values are provided as descriptive representations of the data, since no confirmatory testing is planned.

Document: \\bcnfs02\general\Hdmgener\MEDICAL AFFAIRS 28.02.2017 actualizada\8. SRO ESTUDIOS\RESPIRATORIO\1237-0070 NIS OPTI\11 - Clinical Trial Report\SAP\SAP - V 1.0\SAP OPTI version1.0 29052019.docx

Author:

Version Number: 1.0

Version Date: [29MAY2019]

Template No.: RWI_TP_BIOS0013 Revision 1

Reference: RWI_WI_BIOS0015

Effective Date: 15Jun2018

Copyright © 2018 All rights reserved. The contents of this document are confidential and proprietary to Holdings Inc. and its subsidiaries. Unauthorized use, disclosure or reproduction is strictly prohibited.

8.3 Adjustments for Covariates and Factors to be Included in Analyses

For some of the endpoints, multivariate analyses will be performed using the following covariates and factors. For details of their inclusion in the models, see the specific analysis section. Fixed variables are:

- Age
- Gender

Some optional variables are:

- Smoking history
- Number of exacerbations in the previous year.
- FEV₁ (%) or COPD severity
- FVC (%)
- COPD Risk
- COPD Phenotype
- Gold 2019 Classification A, B, C, D
- Comorbidities as asthma and/or atopy
- CAT category

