16.1.3.1 Current treatment with ICS

Main variable will be presented according to the presence or not of moderate/severe exacerbations in the previous 365 days.

The use of ICS will be analyzed using number of patients in each category and percentages (absolute and relative frequencies) and 95% confidence intervals will be provided based on Wald's (Normal Approximation) method for each group. Percentages will be compared using Chi-Square test or Fisher's Exact test.

Logistic regression will be used to assess the independent contribution of clinical and demographic factors to the estimation of the proportion of patients with COPD who use ICS inadequately. First, univariate and second, multiple logistic regression (MLR) methods will be used to investigate the impact of the following explanatory covariates (patient and disease characteristics) on ICS use.

Potential covariates are:

- Age
- gender
- Smoking history
- Number of exacerbations in the previous year.
- History of asthma (yes/no)
- History of atopy (yes/no)
- COTE index
- COPD GesEPOC 2017 phenotype

Document: \\bcnfs02\general\Hdmgener\MEDICAL AFFAIRS 28.02.2017 actualizada\8. SRO ESTUDIOS\RESPIRATORIO\1237-0070 NIS OPTI\11 - Clinical Trial Report\SAP\SAP - V 1.0\SAP OPTI version1.0 29052019.docx

Author:

Version Number: 1.0

Version Date: [29MAY2019]

Template No.: RWI_TP_BIOS0013 Revision 1

Reference: RWI_WI_BIOS0015

Effective Date: 15Jun2018

Copyright © 2018 All rights reserved. The contents of this document are confidential and proprietary to Holdings Inc. and its subsidiaries. Unauthorized use, disclosure or reproduction is strictly prohibited.

- GOLD 2019 spirometric classifications (1, 2,3, 4)
- GOLD 2019 patient groups (A, B, C, D)
- mMRC score
- CAT - COPD Assessment Test

Backward selection procedures will be applied to generate the final MLR models which consider only covariates in the selection procedure with a p-value <0.1 in the corresponding univariate logistic regression analysis, using inadequate ICS use (yes/no) as response variable. A p-value <0.05 will be used for the covariates to stay in the model in a backward elimination step. Continuous variables can be replaced by categorical variables. Parameters estimated, exp(B) and C95% Wald Confidence Limits for OR will be presented.

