Additionally, logistic regression model will be performed for each age subgroup, using the same procedure described in the previous paragraph. Age subgroups will be adjusted according to the distribution of patients.

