16.2.2 Moderate-to-severe exacerbations in COPD

This analysis consists of the number (count) of moderate-to-severe exacerbations in the previous 1 and 2 years previous to the study visit in COPD patients according to ICS use at time of study visit.

Document: \\bcnfs02\general\Hdmgener\MEDICAL AFFAIRS 28.02.2017 actualizada\8. SRO ESTUDIOS\RESPIRATORIO\1237-0070 NIS OPTI\11 - Clinical Trial Report\SAP\SAP - V 1.0\SAP OPTI version1.0 29052019.docx

Author:

Version Number: 1.0

Version Date: [29MAY2019]

Template No.: RWI_TP_BIOS0013 Revision 1

Reference: RWI_WI_BIOS0015

Effective Date: 15Jun2018

Copyright © 2018 All rights reserved. The contents of this document are confidential and proprietary to Holdings Inc. and its subsidiaries. Unauthorized use, disclosure or reproduction is strictly prohibited.

Patients with missing data related to exacerbations will be excluded from the analysis and number of missing values will be presented.

The objective is to describe the number (total count) of moderate-to-severe exacerbations in one and two years previous to the study visit according to ICS treatment at the time of study visit.

Results will be analyzed with measures of central tendency (mean and median), variability/dispersion (standard deviation and interquartile ranges) and ranges. The number of moderate-to-severe exacerbations will be analyzed using Mann-Whitney U test or Kruskal-Wallis non-parametric tests.

After that, at exploratory level, negative binomial regressions will be used for modelling discrete-count variables, not continuous and limited to non-negative values as the number of moderate-to-severe exacerbations (counts), both for first and second previous years. Covariates included in the model will be those used also in primary analysis, excluding the number of exacerbations in the previous year.

Backward selection procedures will be applied to generate the final model which consider only covariates in the selection procedure with a p-value <0.1 in the corresponding univariate analysis, using number of exacerbations as response variable. A p-value <0.05 will be used for the covariates to stay in the model in a backward elimination step. Continuous variables can be replaced by categorical variables.

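### SAP 8.3 calls age and gender fixed model variables, but 16.1.3.1 and 16.2.2 screen and eliminate them by p-value like any other candidate, so the final models may omit either

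*SAP*

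**What the plan says.** SAP 8.3 divides the covariates for the multivariable analyses into two classes. The first is introduced with "For details of their inclusion in the models, see the specific analysis section. Fixed variables are" and contains age and gender only. The second is introduced with "Some optional variables are" and contains smoking history, prior-year exacerbations, lung function, risk, phenotype, GOLD group, asthma or atopy, and CAT category.

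SAP 16.1.3.1 specifies the logistic models for inadequate ICS use. Under "Potential covariates are" it gives a single list of 12, with age and gender as the first two entries and none marked as forced in. The final models are built by backward selection "which consider only covariates in the selection procedure with a p-value <0.1 in the corresponding univariate logistic regression analysis", and a covariate must then reach p<0.05 to stay. The same section adds that a "logistic regression model will be performed for each age subgroup, using the same procedure described in the previous paragraph".

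SAP 16.2.2 specifies the exploratory negative binomial models for exacerbation counts: "Covariates included in the model will be those used also in primary analysis, excluding the number of exacerbations in the previous year". It applies the same univariate screen at p<0.1, followed by "A p-value <0.05 will be used for the covariates to stay in the model in a backward elimination step".

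The shells for the final models (SAP Tables 26, 27 and 32) show only generic variable rows, with none reserved for age or gender.

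**The concern.** The natural meaning of fixed, when set against optional, is that the variable stays in the model whatever its p-value. The operative rules in 16.1.3.1 and 16.2.2 allow both variables to be removed. Two programmers could each follow the SAP faithfully and deliver different final models.

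The stated purpose of the logistic regression is to assess the independent contribution of clinical and demographic factors. Several candidates, such as the COTE index, mMRC and CAT, plausibly vary with age. If age is dropped because it misses a significance threshold, part of any real age effect is carried by those factors and their odds ratios are no longer adjusted for it. The same can happen to the count coefficients in 16.2.2.

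**Working it through.** **Text comparison**

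| Place in SAP | Status of age and gender | Exempt from selection? |
|---|---|---|
| 8.3 | Fixed, separate from the optional class | Implied |
| 16.1.3.1, overall logistic model | Potential covariates, p<0.1 to enter, p<0.05 to stay | Not stated |
| 16.1.3.1, age-subgroup models | Same procedure | Not stated |
| 16.2.2, negative binomial | Same list less prior-year exacerbations, same thresholds | Not stated |

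**Inputs from the documents (SAP 4.2)**

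- 900 analysed patients; 66% non-exacerbators, 61% of them on ICS.
- The plan's own figures reproduce: 0.66 × 0.61 = 0.403, about 40%; 0.40 ± 1.96 × √(0.40 × 0.60 / 900) = 36.8% to 43.2%; 900 / 0.9 = 1,000.
- The cohort for the logistic model can be read two ways. SAP 16.1.3.2 restricts the inadequate-use analysis to patients without exacerbations: 0.66 × 900 = 594, with 61% on ICS. SAP 16.1.3 places the primary analysis in the FAS, and 16.1.3.1 lists prior-year exacerbations as a covariate, which would have little or no variation among non-exacerbators. That points to 900 patients with 40% events. Both are shown.

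**Chance that age misses p<0.05**

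Assumption: true age log-OR of 0.15 to 0.20 per SD; the documents give no effect size. For a standardised covariate on its own, SE ≈ 1/√(n·p·(1−p)) and the chance of p<0.05 is about Φ(β/SE − 1.96).

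| Cohort | SE | β = 0.15 | β = 0.20 |
|---|---|---|---|
| n = 594, p = 0.61 | 1/√141.3 = 0.084 | Φ(1.78 − 1.96) = 0.43; misses 57% | Φ(2.38 − 1.96) = 0.66; misses 34% |
| n = 900, p = 0.40 | 1/√216 = 0.068 | Φ(2.21 − 1.96) = 0.60; misses 40% | Φ(2.94 − 1.96) = 0.84; misses 16% |

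This treats age alone. In the actual procedure the stay test is conditional on the other covariates retained, so these are approximations to the drop rate.

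**The same for gender**

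Assumptions: OR 1.3; 20% to 50% women. With s the share of women, SE = √[1/(n(1−s)p0(1−p0)) + 1/(n·s·p1(1−p1))], where p0 and p1 differ by log 1.3 on the logit scale and average to the cohort proportion. For n = 594 and s = 0.5, p0 ≈ 0.579 and p1 ≈ 0.641, so SE ≈ 0.169, log 1.3 / SE ≈ 1.56, and the chance of p<0.05 is about 34%. At s = 0.2 it is 23%. In 900 patients the range is 34.5% to 48.5%. With no true effect, gender reaches p<0.05 in 5% of samples.

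**Bias when age is dropped**

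Take a balanced binary factor with no effect of its own, defined by a latent score c × age + error with c = 0.3 to 0.5 (assumed). Its correlation with age is r = c/√(c² + v), where v is the error variance. The mean age difference between its two levels is about 2r√(2/π) SD, and the spurious OR is about exp(β × difference).

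- Normal error (v = 1): r = 0.287 to 0.447; difference 0.46 to 0.71 SD. OR 1.07 to 1.11 at β = 0.15, and 1.10 to 1.15 at β = 0.20.
- Logistic error (v = 3.29): r = 0.163 to 0.266; difference 0.26 to 0.42 SD. OR 1.04 to 1.07 at β = 0.15, and 1.05 to 1.09 at β = 0.20.

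Simulation agrees, reaching 1.16 for a factor present in 20% of patients with normal error, c = 0.5 and β = 0.20. The overall range is roughly 1.04 to 1.16. For scale, the log-OR of a balanced factor in 594 patients has SE 2/√141.3 ≈ 0.17, so even log 1.16 ≈ 0.15 is less than one SE.

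**The case against.** The best reply is that SAP 8.3 defers to the analysis sections for details, and that fixed could mean always on the candidate list while optional means on it or not. The lists are compatible with this: FVC (%) and COPD risk are optional in 8.3 and absent from 16.1.3.1, while age and gender head the list there. The reading is possible but strained. A covariate that is always considered but may always be discarded is not fixed in any sense a model-builder would recognise, and the cross-reference does not settle the matter because the sections it names never mention the status.

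The points about consequence carry more weight. The lung function candidate in 16.1.3.1 is the GOLD class, based on FEV1 as a percentage of predicted. The age-subgroup models give some coarse control for age, and Table 25 shows age and gender univariately in any case. SAP 8.2 treats p-values as descriptive, 16.2.2 is labelled exploratory, and protocol 9.9 disclaims causal conclusions. All of this stands and limits the point.

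A reader might infer that the reported odds ratios will be seriously confounded. The documents do not support that: they give no age effect and no relation between age and the other factors, the bias arises only if age is dropped, and under the assumptions above it is modest. Nor does the point concern odds ratios throughout, since the negative binomial models yield count coefficients.

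**Conclusion.** The inconsistency is real and lies in the current SAP text: 8.3 fixes age and gender, and no analysis section protects them from selection. A final model without one or both is a realistic outcome under the written rule.

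The probabilities and the bias are illustrations that rest on assumed effects, on the choice between a 594-patient and a 900-patient cohort, and on single-covariate approximations. The primary proportion and its confidence interval do not depend on these models. This is a minor point, worth correcting because the remedy follows the plan's own designation and costs almost nothing.

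**What to change.** In SAP 16.1.3.1 and 16.2.2, state that age and gender are kept in the overall multivariable models regardless of p-value, and that the p<0.1 screen and p<0.05 elimination apply only to the other covariates. For the age-subgroup logistic models, state that gender is kept and that adjustment for remaining age differences within a subgroup is optional, since the stratification has already narrowed age. Whether age enters as continuous or categorical can stay as the SAP allows. Reserve rows for age and gender in Tables 26 and 32, and for gender in Table 27.

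If the sponsor never meant to force these variables in, the alternative is to remove the word fixed from 8.3. That restores consistency but gives up the adjustment.

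The cost is a sentence in each section, a setting in the model code, and two degrees of freedom per overall model if age is continuous (more if it is grouped). No new data are needed, and the sample size does not change.

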8.4 Missing data

Missing data will not be imputed, except in those variables described in their scoring system.

According to general analysis, if patients have missing values for an outcome, those patients will be excluded for that outcome's analysis.

Document: \\bcnfs02\general\Hdmgener\MEDICAL AFFAIRS 28.02.2017 actualizada\8. SRO ESTUDIOS\RESPIRATORIO\1237-0070 NIS OPTI\11 - Clinical Trial Report\SAP\SAP - V 1.0\SAP OPTI version1.0 29052019.docx

Author:

Version Number: 1.0

Version Date: [29MAY2019]

Template No.: RWI_TP_BIOS0013 Revision 1

Reference: RWI_WI_BIOS0015

Effective Date: 15Jun2018

Copyright © 2018 All rights reserved. The contents of this document are confidential and proprietary to Holdings Inc. and its subsidiaries. Unauthorized use, disclosure or reproduction is strictly prohibited.

9. OUTPUT PRESENTATIONS

Tables and Figures on page 39 describe the presentations for this study and therefore the format and content of the summary TLFs to be provided by RWES Biostatistics.

Document: \\bcnfs02\general\Hdmgener\MEDICAL AFFAIRS 28.02.2017 actualizada\8. SRO ESTUDIOS\RESPIRATORIO\1237-0070 NIS OPTI\11 - Clinical Trial Report\SAP\SAP - V 1.0\SAP OPTI version1.0 29052019.docx

Author: Version Number: 1.0
Version Date: [29MAY2019]

Template No.: RWI_TP_BIOS0013 Revision 1 Reference: RWI_WI_BIOS0015

Effective Date: 15Jun2018

Copyright © 2018 All rights reserved. The contents of this document are confidential and proprietary to Holdings Inc. and its subsidiaries. Unauthorized use, disclosure or reproduction is strictly prohibited.

10. DISPOSITION AND WITHDRAWALS

All subjects who provide informed consent will be accounted for in this study. Subject disposition, withdrawals, and protocol violations (as defined in section 6.2), including inclusion and exclusion criteria will be presented for all enrolled patients.

11. DEMOGRAPHIC AND OTHER BASELINE CHARACTERISTICS

Demographic data and other baseline characteristics will be presented for the FAS. General statistical testing will be carried out for demographic or other baseline characteristics.

The following demographic and other baseline characteristics will be reported for this study:

- Age in study visit
- Sex
- Ethnicity
- Weight (kg), Height (cm), Body mass index (BMI) (kg/m^2) and categories
- Tobacco use (no-smoker, ex-smoker, smoker, packs/year)
- Time since diagnosis (years) - calculated relative to date of visit

11.1 Derivations

Derived variables are specified in section 7.2. Common Calculations on page 15 in this SAP.

12. SURGICAL AND MEDICAL HISTORY

Neither surgical nor medical history are collected in the eCRF.

13. COMORBIDITIES

Comorbidities are collected according to COTE index, plus asthma and athopy. Comorbidities will be presented for the FAS.

Document: \\bcnfs02\general\Hdmgener\MEDICAL AFFAIRS 28.02.2017 actualizada\8. SRO ESTUDIOS\RESPIRATORIO\1237-0070 NIS OPTI\11 - Clinical Trial Report\SAP\SAP - V 1.0\SAP OPTI version1.0 29052019.docx

Author:

Version Number: 1.0

Version Date: [29MAY2019]

Template No.: RWI_TP_BIOS0013 Revision 1

Reference: RWI_WI_BIOS0015

Effective Date: 15Jun2018

Copyright © 2018 All rights reserved. The contents of this document are confidential and proprietary to Holdings Inc. and its subsidiaries. Unauthorized use, disclosure or reproduction is strictly prohibited.

14. MEDICATIONS

Medications will be presented for the FAS and coded using the WHO Drug Dictionary (WHO-DD) and Anatomical Therapeutic Chemical (ATC) class coding (including ATC Level 3).

Medications (antibiotics and corticosteroids) used for exacerbations, will be considered only if start date is in the two years previous to the study visit. Medications started previously will not be considered for analysis due to the exacerbations are not included in the study period.

15. STUDY MEDICATION EXPOSURE

Patients in this study will have been prescribed a treatment for their COPD. They could have been prescribed ICS or not. Prescription of the treatments will have been done under the sole responsibility of the healthcare professional and before the study initiation visit.

16. PRIMARY OUTCOMES

16.1 Primary Endpoint

The primary endpoint for a patient, currently on ICS, is absence or presence of moderate/severe exacerbation in the year prior to the study visit.

16.1.1 Data Variables and Derivation

The data will be obtained from medical charts and it will be collected in “treatments” section (all treatment combinations including ICS will be considered as “yes” and also ICS discontinuation the same date of the study visit will be considered as “yes”). Treatments have to be started previously to the study visit and it have to be ongoing or stopped the same day of the study visit.

16.1.2 Missing Data Methods for Primary Endpoint

Missing data will not be imputed. If patients have missing values for this outcome, those patients will be excluded for the analysis and number of missing values will be presented.

Document: \\bcnfs02\general\Hdmgener\MEDICAL AFFAIRS 28.02.2017 actualizada\8. SRO ESTUDIOS\RESPIRATORIO\1237-0070 NIS OPTI\11 - Clinical Trial Report\SAP\SAP - V 1.0\SAP OPTI version1.0 29052019.docx

Author:

Version Number: 1.0

Version Date: [29MAY2019]

Template No.: RWI_TP_BIOS0013 Revision 1

Reference: RWI_WI_BIOS0015

Effective Date: 15Jun2018

Copyright © 2018 All rights reserved. The contents of this document are confidential and proprietary to subsidiaries. Unauthorized use, disclosure or reproduction is strictly prohibited.

Holdings Inc. and its

16.1.3 Primary Analysis of Primary Endpoints

The primary analysis will consist of the proportion of patients, currently on ICS, who did not have or had moderate/severe exacerbation in the year prior to the study visit. The primary analysis will be performed for the FAS.

16.1.3.1 Current treatment with ICS

Main variable will be presented according to the presence or not of moderate/severe exacerbations in the previous 365 days.

The use of ICS will be analyzed using number of patients in each category and percentages (absolute and relative frequencies) and 95% confidence intervals will be provided based on Wald's (Normal Approximation) method for each group. Percentages will be compared using Chi-Square test or Fisher's Exact test.

Logistic regression will be used to assess the independent contribution of clinical and demographic factors to the estimation of the proportion of patients with COPD who use ICS inadequately. First, univariate and second, multiple logistic regression (MLR) methods will be used to investigate the impact of the following explanatory covariates (patient and disease characteristics) on ICS use.

Potential covariates are:

- Age
- gender
- Smoking history
- Number of exacerbations in the previous year.
- History of asthma (yes/no)
- History of atopy (yes/no)
- COTE index
- COPD GesEPOC 2017 phenotype

Document: \\bcnfs02\general\Hdmgener\MEDICAL AFFAIRS 28.02.2017 actualizada\8. SRO ESTUDIOS\RESPIRATORIO\1237-0070 NIS OPTI\11 - Clinical Trial Report\SAP\SAP - V 1.0\SAP OPTI version1.0 29052019.docx

Author:

Version Number: 1.0

Version Date: [29MAY2019]

Template No.: RWI_TP_BIOS0013 Revision 1

Reference: RWI_WI_BIOS0015

Effective Date: 15Jun2018

Copyright © 2018 All rights reserved. The contents of this document are confidential and proprietary to Holdings Inc. and its subsidiaries. Unauthorized use, disclosure or reproduction is strictly prohibited.

- GOLD 2019 spirometric classifications (1, 2,3, 4)
- GOLD 2019 patient groups (A, B, C, D)
- mMRC score
- CAT - COPD Assessment Test

Backward selection procedures will be applied to generate the final MLR models which consider only covariates in the selection procedure with a p-value <0.1 in the corresponding univariate logistic regression analysis, using inadequate ICS use (yes/no) as response variable. A p-value <0.05 will be used for the covariates to stay in the model in a backward elimination step. Continuous variables can be replaced by categorical variables. Parameters estimated, exp(B) and C95% Wald Confidence Limits for OR will be presented.

Additionally, logistic regression model will be performed for each age subgroup, using the same procedure described in the previous paragraph. Age subgroups will be adjusted according to the distribution of patients.

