9.2 SETTING

Approximately 1,000 patients with COPD are planned to be included in the study. To minimize selection bias at the patient level, the first 5 consecutive patients from each site who met all inclusion criteria and none of the exclusion criteria will be enrolled from approximately April 2018 and during one year.

It is necessary to ensure that study population is representative of the entire national territory. Therefore, patients will be recruited from primary care centers in different geographical areas according to the distribution of the overall population in this area. Site selection will be performed in order to secure representativeness of the COPD population.

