9.2.1 Study sites

Approximately 200 primary care centers, who regularly attend COPD patients, will be selected to participate. It is necessary to ensure that study population is representative of the entire national territory, including sites of all 17 autonomous communities. Number of sites/patients in each Autonomous Communities will be approached according COPD population distribution extracted from Spanish Statistic National Institute (data available for 2014). Site feasibility assessments will be performed by the CRO during the site selection process.

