9.5 STUDY SIZE

Due to the descriptive design of the proposed non interventional study, a formal sample size calculation has not been performed based on statistical power and protection for type I error.

In previously published studies in usual clinical practice in primary care in Spain (4), 66% of patients are non-exacerbators and of these, 61% are treated with ICS, therefore approximately 40% of all patients are currently treated with ICS without having exacerbations in the prior year.

Assuming a sample size of 900 patients and 40% of the patients are treated with ICS at the study visit and did not have a moderate or severe COPD exacerbation in the prior year, the 95% confidence interval for this proportion would be between 36.8% (lower limit) and 43.2% (upper limit). To account for a 10% drop-out rate (patients with inconsistent, incomplete or missing data), the sample size becomes 1,000 patients.

Table 9.5:1 Scenario for estimated proportions by 95% CI

Scenario for estimated proportions by 95% confidence intervals (95% CI)

	1	2	3	4	5	6	
Expected proportion		0.4			0.5		
Lower and Upper limit of 95% CI	(0.37;0.43)	(0.368;0.432)	(0.365;0.435)	(0.47;0.53)	(0.468;0.532)	(0.465;0.535)	
Precision of estimation	0.03	0.032	0.035	0.03	0.032	0.035	
N (at final analysis)	1000	900	753	1042	938	784	
Dropout	10%	1112	1000	838	1159	1043	872

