16.1.3.2 Inadequate use of ICS

As a part of main analysis, inadequate use of ICS will be presented as in the previous section 16.1.3.1. Current treatment with ICS. This analysis will be presented only for patients without exacerbations in the previous year. This cohort will be used because only patients without exacerbations can receive ICS without requiring it, which is, making an inappropriate use of the treatment.

Document: \\bcnfs02\general\Hdmgener\MEDICAL AFFAIRS 28.02.2017 actualizada\8. SRO ESTUDIOS\RESPIRATORIO\1237-0070 NIS OPT\11 - Clinical Trial Report\SAP\SAP - V 1.0\SAP OPTI version1.0 29052019.docx

Author:

Version Number: 1.0

Version Date: [29MAY2019]

Template No.: RWI_TP_BIOS0013 Revision 1

Reference: RWI_WI_BIOS0015

Effective Date: 15Jun2018

Copyright © 2018 All rights reserved. The contents of this document are confidential and proprietary to Holdings Inc. and its subsidiaries. Unauthorized use, disclosure or reproduction is strictly prohibited.

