19.3 Listings

All listings will be ordered by the following: group (ICS/non-ICS, etc.), center-subject ID, and date (where applicable).

Document: \\bcnfs02\general\Hdmgener\MEDICAL AFFAIRS 28.02.2017 actualizada\8. SRO ESTUDIOS\RESPIRATORIO\1237-0070 NIS OPTI\11 - Clinical Trial Report\SAP\SAP - V 1.0\SAP OPTI version1.0 29052019.docx

Author:

Version Number: 1.0

Version Date: [29MAY2019]

Template No.: RWI_TP_BIOS0013 Revision 1

Reference: RWI_WI_BIOS0015

Effective Date: 15Jun2018

Copyright © 2018 All rights reserved. The contents of this document are confidential and proprietary to Holdings Inc. and its subsidiaries. Unauthorized use, disclosure or reproduction is strictly prohibited.

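### The confidence intervals for ICS use treat patients as independent, although patients are sampled five per site from about 200 sites

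*SAP*

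**What the plan says.** **Sampling.** Protocol 9.2 states that "the first 5 consecutive patients from each site who met all inclusion criteria and none of the exclusion criteria will be enrolled". Protocol 9.2.1 adds: "Approximately 200 primary care centers, who regularly attend COPD patients, will be selected to participate".

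**Precision.** Protocol 9.5 and SAP 4.2 assume 900 analysed patients, 40% of them on ICS and free of moderate or severe exacerbation in the prior year. They give a 95% interval of 36.8% to 43.2%. A 10% loss brings recruitment to 1,000, which is 200 sites of 5.

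**Analysis.** SAP 16.1.3 defines the primary analysis as "the proportion of patients, currently on ICS, who did not have or had moderate/severe exacerbation in the year prior to the study visit". For ICS use by exacerbation group, SAP 16.1.3.1 says that "95% confidence intervals will be provided based on Wald's (Normal Approximation) method for each group", and SAP 16.2.1 repeats this for two years. Table 24 reports ICS use as column percentages, each with a 95% interval. Table 5 asks for intervals for current ICS treatment, for exacerbation in the previous year and for inadequate ICS use, without naming a method.

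**Site.** Site is in neither covariate list (SAP 8.3, 16.1.3.1). SAP 8.1 ties the handling of bias to missing values, and the limitations in protocol 9.9 do not mention clustering. In the analysis plan, centre appears only in the sort order of listings (SAP 19.3).

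**The concern.** The Wald variance p(1−p)/n is right only if patients are independent. Protocol 9.1 and 9.3.1 describe treatment as following the physician's own prescribing habits and responsibility. Patients of one centre share one or a few prescribers, so some likeness in ICS use within a site is plausible. The plan sets that likeness to zero without saying so.

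The study is descriptive, and SAP 8.2 says that "P-values are provided as descriptive representations of the data, since no confirmatory testing is planned". The confidence intervals are therefore its main inferential output.

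The intervals are not equally exposed:

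1. ICS use in all patients (Table 5) and within each exacerbation column (Table 24) is exposed directly if prescribing clusters.
2. The joint proportion behind 36.8% to 43.2% (on ICS and no exacerbation) is exposed less, because only part of its variation comes from prescribing.
3. The proportion without exacerbation among ICS users, and Table 5's exacerbation interval, are exposed only if exacerbations or their recording cluster by site.

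Table 5's interval for inadequate use is left out. Its denominator is not settled: SAP 7.2.14 classifies patients by guideline adherence, SAP 16.1.3.2 says "This analysis will be presented only for patients without exacerbations in the previous year", and Table 5 uses a third wording.

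**Working it through.** **Inputs from the documents.** About 200 sites, 5 recruited per site, 10% loss (900/200 = 4.5 analysed per site), p = 0.40, 66% non-exacerbators, 61% ICS use among them.

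**Assumed.** ICC of 0.01, 0.05, 0.10 and 0.20; 61% ICS use also among exacerbators.

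**1. The plan's figure.** 1.96 × √(0.4 × 0.6/900) = 0.0320, giving 36.8% to 43.2%. Also 0.66 × 0.61 = 0.403 and 900/0.9 = 1,000. The stated interval is exactly the independent-patient result, a design effect of 1.

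**2. Formulas.** DEFF = 1 + (m − 1) × ICC. The half-width is multiplied by √DEFF. The unadjusted interval covers 2Φ(1.96/√DEFF) − 1.

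**3. ICS use.** For all patients m = 4.5. For the Table 24 columns, the size-weighted number per site is 1 + 3.6 × 0.66 = 3.38 (no exacerbation, n about 594) and 1 + 3.6 × 0.34 = 2.22 (exacerbation, n about 306), where 3.6 = 4 × 0.9. Corrected half-width in points, with coverage of the planned interval in brackets:

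| Interval | Planned | ICC 0.01 | 0.05 | 0.10 | 0.20 |
|---|---|---|---|---|---|
| Table 5, all patients | ±3.19 | ±3.24 (94.6%) | ±3.45 (92.9%) | ±3.70 (90.8%) | ±4.15 (86.7%) |
| Table 24, no exacerbation | ±3.92 | ±3.97 (94.7%) | ±4.15 (93.6%) | ±4.36 (92.2%) | ±4.76 (89.3%) |
| Table 24, exacerbation | ±5.46 | ±5.50 (94.9%) | ±5.63 (94.3%) | ±5.79 (93.6%) | ±6.10 (92.1%) |

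**4. Joint proportion.** If only prescribing clusters, with ICC r, the joint ICC is 0.66² × 0.61 × 0.39 × r/(0.4026 × 0.5974) = 0.431r. For r = 0.01, 0.05, 0.10 and 0.20, DEFF = 1.015, 1.075, 1.151 and 1.302. The half-width is ±3.22, ±3.32, ±3.43 and ±3.65, and the effective n is 887, 837, 782 and 691. If the joint outcome itself has those ICCs, the half-width is ±3.26, ±3.47, ±3.72 and ±4.17. Reaching ±3.5 needs a joint ICC of 0.056 (prescribing 0.130).

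**5. Simulation.** 200 sites of 4 or 5 patients, beta-distributed site rates, 6,000 runs per setting. Coverage of the Wald interval when prescribing clusters and exacerbations do not:

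| Quantity | ICC 0.01 | 0.05 | 0.10 | 0.20 |
|---|---|---|---|---|
| ICS use, all patients | 94.6% | 93.6% | 91.1% | 86.9% |
| ICS use, no exacerbation | 94.3% | 93.4% | 92.2% | 88.9% |
| Joint proportion | 94.8% | 94.4% | 93.3% | 91.4% |
| No exacerbation among ICS users | 94.8% | 94.8% | 95.0% | 94.6% |

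Mean site-clustered half-widths are ±3.26, ±3.48, ±3.73 and ±4.19 for ICS use in all patients, ±3.99, ±4.16, ±4.38 and ±4.78 for the non-exacerbator column, and ±3.98 throughout for ICS users (Wald ±3.96). A separate 5,000-run simulation agrees within about 1.5 points. With 80% ICS use among exacerbators, coverage for all patients is 94.4, 92.4, 91.1 and 86.9%.

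**6. If exacerbations also cluster, at ICC 0.05 or 0.10.** The interval among ICS users becomes about ±4.2 or ±4.4, with Wald coverage 93.1–94.0% or 91.8–92.4%. Table 5's exacerbation interval goes from ±3.1 to ±3.4 or ±3.6, with coverage 92.9–93.3% or 90.3–91.2%.

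Site-clustered intervals covered 94.0–95.7% in all 30 settings simulated.

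**The case against.** **The size is assumed.** No ICC is given. At 0.01 nothing material happens, at 0.05 the largest change is from ±3.2 to ±3.5 points, and coverage of 87–91% needs an ICC of 0.10 to 0.20. This stands, and it is why the observed ICC should be reported.

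**The primary outcome as worded is untouched** unless exacerbations or their recording cluster, which is a second assumption. This also stands. The exposed intervals are nevertheless those that SAP 16.1.3.1 places in the primary analysis, through Table 24.

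**The plan already shows wider precision.** SAP Table 1 runs to ±3.7 points (n = 674) at p = 0.40, and every effective n in step 4 exceeds 674. That is true of the joint proportion, but those rows stand for smaller samples. They do not correct the intervals that will be reported.

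**Restating the precision changes no decision.** The SAP is dated 29 May 2019, after the planned end of data collection in April 2019. This is correct; the sentence only helps the reader interpret the result. A joint ICC of 0.10 or 0.20 would also need a prescribing ICC of about 0.23 or 0.46, so the sentence must say which ICC it means.

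**Other limits.** The exacerbation column of Table 24 is the least affected. Allocating sites by autonomous community could recover part of the loss, but the documents give no figure. The profile tables (6 to 23) carry no intervals, so the point does not reach the descriptive profile itself.

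**Conclusion.** The concern holds as a conditional statement. The design is a cluster sample, the planned precision and the Wald intervals assume independence, and neither document adjusts for site. Any positive within-site correlation in ICS use puts the ICS-use intervals below 95% coverage.

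The shortfall is about one to two points of coverage at ICC 0.05, about four at 0.10 and about eight at 0.20 for ICS use in all patients. It is smaller in the Table 24 columns and for the joint proportion. These sizes rest on assumed ICCs, about 4.5 analysed patients per site, and 61% ICS use among exacerbators as well. The change should be made because it is cheap and these intervals carry the inference; the study's conclusions do not depend on it. The tests are little affected and need no change.

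**What to change.** In SAP 16.1.3.1 and 16.2.1, replace the Wald sentence by:

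> 95% confidence intervals for proportions will be computed with site as the cluster (SAS PROC SURVEYFREQ, CLUSTER site; t with number of sites minus 1 degrees of freedom), keeping the whole FAS and treating exacerbation group or ICS use as a domain.

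This covers the one-year and two-year intervals. Apply it to every interval for a proportion in Tables 5 and 24, and to the proportion without exacerbation among ICS users. That last interval needs a line of its own, because Table 24 shows column percentages and Table 31 shows no interval. Report the observed site ICC for ICS use and for exacerbation in the prior year.

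In SAP 4.2, add:

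> The ±3.2 points assume no correlation between patients of the same site; for a site ICC of 0.01, 0.05, 0.10 or 0.20 in this joint outcome they become about ±3.3, ±3.5, ±3.7 or ±4.2; n is unchanged.

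Rao-Scott tests and site-robust standard errors for the regression models are optional.

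**Cost.** Three SAP sentences and one procedure in SAS 9.4, the software already named. No new data are needed, since centre is part of the subject identifier. No protocol change is needed either, because protocol 9.7 asks for intervals where appropriate and names no method. The downside is slightly wider intervals and a less favourable stated precision. If the observed ICC is near zero, the intervals barely move.
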